#### Other safety data:

For other safety data, data from early discontinuation should be compared to theoretical visits dates. Only assessments within the window of theoretical date +/-14 days will be used for analyses, if it is planned to have a such assessment at this visit and no other assessment is in the window. If a subject discontinued in the extension treatment period, date will be compared to the theoretical visit dates in extension treatment period as described in Table 3. If a subject discontinued in the extension follow-up period, date will be compared to the theoretical visit dates in extension Follow-up period from Table 4.

For unscheduled safety assessments, if the assessment occurs within a window of theoretical date +/- 14 days for a planned eCRF visit for which it was planned per protocol to have such assessment, and no assessment was done for that visit, the assessment will be assigned to that visit. If the assessment is equally distant from two eCRF visits with no corresponding safety assessment, the assessment will be assigned to the next visit.

Sponsor:	ObsEva		
Protocol:	19-OBE2109-005		
Document Version No.:	1.0	Document Date:	18-MAY-2021

For biopsy, DXA assessment or laboratory assessment, if an assessment has been assigned in external data to a follow-up visit of the main study for subjects who entered in the extension study, the visit of assessment should be reassigned with the same rules described above for unscheduled safety assessment.

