## 4.2.12. Last extension treatment administration date, End of extension Study date and Period definitions

The last extension treatment administration date will be defined as the date from the treatment termination reported in the extension period eCRF page. If this date is missing, the last date with a drug intake in the eDiary that is inferior or equal to Month 12 visit or the last available date with a drug intake in the eDiary if the subject discontinued the extension treatment will be used.

For subjects who entered the extension, the end of the extension study date will be the last assessment date in the extension study defined as last assessment recorded in the eCRF (excluding end date of adverse events and concomitant medications) or ediary date.

Note:

- For summaries by visit (efficacy or safety), the Month 6 assessments will be included in the main study analyses. For Adverse Events, Concomitant Medications and Daily diaries data collected on the Month 6 date will be part of the extension for subjects entering the extension study, and will be part of the main Follow-up period for subjects entering the main study follow-up period.
- For Adverse Events, Concomitant Medications and Daily diaries, data collected on the Month 12 date will be part of the Extension Follow-up period for subjects entering the Extension follow-up period.

The extension treatment period will be defined as Month 6 up to (Month 12 date -1) or treatment discontinuation date.

The extension follow-up period will be defined as the Month 12 date or (treatment discontinuation date+1) up to the extension follow-up end date (for subjects who entered the extension follow-up).

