#### 4.8.4. Laboratory Data

Clinical laboratory values will be expressed using conventional SI units.

Hematology, coagulation parameters, chemistry and lipids were assessed at screening and at each visit during the extension treatment period (from M7 to M12), as well as at the M1 ExtFU and M3 ExtFU visits.

E2, progesterone (P4) and LH were assessed at each visit during the extension treatment period (from M6 to M12), as well as at M1 ExtFU and M3 ExtFU visits.

Serum levels of sex hormone-binding globulin (SHBG) were assessed on Month 6, Month 9 and Month 12 visits.

Blood samples were to be analyzed by the central laboratory. Due to the covid-19 situation, some samples may be collected by local laboratories.

For Hematology, coagulation parameters, chemistry and lipids, the actual value, change from baseline and change from baseline 2 (only for the subjects who are in the placebo arm in the main study) will be summarized for each visit for each treatment group. In the event of repeated values, the last non-missing value per study day/time will be used.

Evaluation of shifts for changes from baseline and for changes from baseline 2 (only for the subjects who are in the placebo arm in the main study) to all visits according to the normal ranges with categories "Low", "Normal", "High" and according to normal/abnormal/abnormal clinically significant information collected otherwise, will be provided.

For Liver Function Test (LFT) parameters (ALT, AST, ALP, total bilirubin, direct bilirubin, indirect bilirubin, GGT, LDH, albumin and Creatine Kinase), evaluation of shifts for changes from baseline will be extended by the worst (highest) on-treatment value (including unscheduled assessments) according to the normal ranges with categories "Low", "Normal", "High" will be provided.

For the lipid panel (Triglycerides, HDL, LDL, Total Cholesterol, LDL/HDL ratio), the percent change from baseline and the percent change from baseline 2 (only for the subjects who are in the placebo arm in the main study) to each on-study visit will also be summarized.

For serum levels of P4, SHBG and LH, only the actual values at each time point will be summarized. Note: in the event of repeated values, the last non-missing value per study day/time will be used.

Note that no serum levels of E2 is measured for subjects in extension study due to the early termination study.

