For P4, since P4 above 10 nMol/L may suggest luteal activity and hence ovulation, the proportion of subjects with P4 >10.0 nMol/L at least once from Month 6 to Month 12 will also be provided in tables.

The number and percentage of subjects with cholesterol values in the following categories

• LDL ≥ 160 mg/dL

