- Table 14.4.5.8 Lipids Parameters Shifts from Baseline Based on Clinical Findings from Month 7 up to Month 6 Extension Follow-up – Extension Safety Analysis Set
- Table 14.4.5.9 Lipids Parameters Shifts from Baseline 2\* based on Clinical Findings from Month 7 up to Month 6 Extension Follow-up – Extension Safety Analysis Set – subset of subjects who are in the placebo arm (actual arm) in the main study
- Table 14.4.5.10 Lipids Parameters Shifts from Baseline Based on Normal Ranges from Month 7 up to Month 6 Extension Follow-up – Extension Safety Analysis Set
- Table 14.4.5.11 Lipids Parameters Shifts from Baseline 2\* based on Clinical Findings from Month 7 up to Month 6 Extension Follow-up – Extension Safety Analysis Set – subset of subjects who are in the placebo arm (actual arm) in the main study
- Table 14.4.6.1 Serum levels of P4, SHGB and LH from Month 7 up to Month 6 Extension Follow-up – Extension Safety Analysis Set
- Table 14.4.6.3 Proportions of Subjects with P4 at Least once >10.0 nMol/L from Month 6 to Month 12 Extension Safety Analysis Set
- Table 14.4.7.1 Vital Signs by Visit from Month 7 up to Month 6 Extension Follow-up Extension Safety Analysis Set
- Table 14.4.8.1 Physical Examination Findings from Month 9 up to Month 6 Extension Followup – Extension Safety Analysis Set
- Table 14.4.8.2 Physical Examination Findings Shifts from Baseline from Month 9 up to Month 6 Extension Follow-up – Extension Safety Analysis Set

Sponsor:	ObsEva		
Protocol:	19-OBE2109-00	5	
Document Version No.:	1.0	Document Date:	18-MAY-2021

- Table 14.4.8.3 Physical Examination Findings Shifts from Baseline 2\* from Month 9 up to Month 6 Extension Follow-up – Extension Safety Analysis Set – subset of subjects who are in the placebo arm (actual arm) in the main study
- Table 14.4.9.1 ECG QTcF by Visit from Month 7 up to Month 6 Extension Follow-up Extension Safety Analysis Set
- Table 14.4.9.2 ECG Findings from Month 7 up to Month 6 Extension Follow-up Extension Safety Analysis Set
- Table 14.4.10.1 Gynecological Examination Findings by Visit from Month 9 up to Month 6 Extension Follow-up – Extension Safety Analysis Set
- Table 14.4.11.2 Breast Examination Findings by Visit from Month 9 up to Month 6 Extension Follow-up Extension Safety Analysis Set
- Table 14.4.12.1 Endometrial Biopsy Findings by visit from Month 12 up to Month 6 Extension Follow-up – Extension Safety Analysis Set

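### The at-least-once progesterone count opens at Month 6, so read literally a sample taken on placebo can class a switched woman as positive in the extension table

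*SAP*

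**What the plan says.** SAP section 4.8.4 treats P4 above 10 nmol/L as a possible sign of luteal activity, and hence of ovulation. It adds that "the proportion of subjects with P4 >10.0 nMol/L at least once from Month 6 to Month 12 will also be provided in tables". In SAP section 7.2, Table 14.4.6.3 is titled "Proportions of Subjects with P4 at Least once >10.0 nMol/L from Month 6 to Month 12". The by-visit table for the same hormone, Table 14.4.6.1, has a different start: "Serum levels of P4, SHGB and LH from Month 7 up to Month 6 Extension Follow-up".

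The sampling sentence in 4.8.4 reads "E2, progesterone (P4) and LH were assessed at each visit during the extension treatment period (from M6 to M12"; the sentence before it gives Month 7 as the start for hematology, coagulation, chemistry and lipids.

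Two statements in SAP section 4.2.12 bear on the window. One is a note: "For summaries by visit (efficacy or safety), the Month 6 assessments will be included in the main study analyses". The other defines the period: "The extension treatment period will be defined as Month 6 up to (Month 12 date -1) or treatment discontinuation date".

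The protocol fixes the order of events at Month 6. Under sections 10.1 and 10.2.1.1, all Month 6 assessments come first, then the extension consent, then the new kits, then the dose taken at the site. Appendix A, note 2, assigns the Month 6 assessments, other than consent and eligibility, to the main study.

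**The concern.** The count is meant to show whether luteal activity occurs during extension treatment. For a woman who took placebo in the main study, the Month 6 P4 value precedes any linzagolix. It is normally the value that SAP section 4.2.11 calls Baseline 2. If it counts, the two Placebo/linzagolix columns can show luteal activity that occurred on placebo under an extension treatment label.

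Comparability between columns is also affected. For continuing women the Month 6 sample follows six months of linzagolix, so the same row of the table would mix an off-drug sample with an on-drug one.

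Short exposure makes this more relevant. SAP section 2.1 reports all subjects regardless of treatment duration, so a switched woman with no post-dose P4 sample could be classified on her placebo value alone.

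**Working it through.** There is no plan figure to reproduce: neither document gives a P4 rate, a target or a denominator for this proportion. The check is on text and timing, followed by what arithmetic can bound.

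**1. Is Month 6 inside the written window?**
- Named in the 4.8.4 sentence and in the Table 14.4.6.3 title: yes.
- Inside the extension treatment period as 4.2.12 defines it: yes, because that period opens at Month 6.
- Removed by another sentence: not clearly. The 4.2.12 note concerns by-visit summaries, and an at-least-once count is not one.
- Restricted to treatment by its own wording: no. The liver-test worst-value summary in 4.8.4 says on-treatment, and the adverse event definition in 4.8.2 is tied to the first extension dose. The P4 sentence has neither limit.

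**2. Share of pre-active samples for a switched woman.** P4 is scheduled at every visit, so from Month 6 to last visit *m* there are *m* − 6 + 1 samples, one of them pre-active.

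| Last visit | Samples | Pre-active share |
|---|---|---|
| Month 7 | 2 | 1/2 = 50% |
| Month 9 | 4 | 1/4 = 25% |
| Month 12 | 7 | 1/7 = 14% |

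**3. Effect among women with at least one post-dose sample.** Let *q* be the proportion positive at Month 6 and *p* the proportion positive at least once afterwards, in the same women. Counting Month 6 adds those positive at Month 6 and never again. That addition lies between max(0, *q* − *p*) and min(*q*, 1 − *p*). It is never negative, never exceeds *q*, and can be zero.

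An illustration, resting wholly on assumed rates: take independent visits, six post-dose samples and per-visit positivity *r* on drug. Then *p* = 1 − (1 − *r*)^6 and the addition is *q*(1 − *r*)^6.
- *r* = 0.02: *p* = 11.4%; the addition is 8.9 points at *q* = 0.10 and 44.3 points at *q* = 0.50.
- *r* = 0.10: *p* = 46.9%; the addition is 5.3 points at *q* = 0.10 and 26.6 points at *q* = 0.50.

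The width of this range shows how little can be said without data.

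**4. Effect of women with only a Month 6 sample.** Take a hypothetical 10 switched women. Eight have post-dose samples, two of these eight are positive after dosing, and none of the eight is positive at Month 6 alone. The other two have only Month 6. Restricting to post-dose samples gives 2/8 = 25%. With Month 6 counted:
- both Month-6-only women negative: 2/10 = 20%, lower;
- both positive: 4/10 = 40%, higher.

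**5. Weight of one woman.** Planned maximum per switch group, assuming equal retention across arms: 450/3 × 0.8 × 0.8 / 2 = 48. One woman positive only at Month 6 moves the proportion by 1/48 = 2.1 points, or by 1/10 = 10 points in an assumed group of 10.

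**6. Early stoppers.** For discontinuation samples, section 4.2.10 says the "date will be compared to the theoretical visit dates in extension treatment period as described in Table 3", with ±14 days and only if no other assessment is in the window. Table 3 lists Month 6 at Day 169, so its window ends at Day 183 (169 + 14); the Month 7 window begins there too (197 − 14). A post-dose sample before Day 183 falls only in the Month 6 window, which the placebo-phase sample already occupies, so it could be set aside.

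**The case against.** The best defence is that Month 6 to Month 12 is simply the SAP's label for the extension treatment period, as used in 4.8.2 and 4.8.7 and in the adverse event and concomitant medication table titles. On that view Month 6 laboratory values belong to the main study. Section 4.2.12 supports this: it names the data types whose Month 6 records move into the extension (adverse events, concomitant medications, daily diaries), and laboratory values are not among them.

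Other sections point the same way. SHBG is described as sampled at Month 6, yet Table 14.4.6.1 starts at Month 7. Physical, gynecological and breast examinations and ultrasound all name Month 6 in the text, yet their tables start at Month 9. The C-SSRS text in 4.8.10 says Month 6 while Table 14.4.15.1 starts at Month 7.

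Much of this stands. A reader might infer that the SAP consistently keeps Month 6 in extension summaries; it does not. The 4.8.4 sampling sentence describes when blood was drawn, and Table 3 places early-discontinuation samples without deciding whether the scheduled Month 6 value counts. The C-SSRS mismatch is a matter of wording alignment only.

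The defence does not settle this count, however. The labelled period itself opens at Month 6, the by-visit note does not reach an at-least-once count, and here, unlike in the C-SSRS case, the table title names Month 6 as well. The programmer is left with two defensible readings.

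**Conclusion.** The point holds as a minor correction. The written rule, read literally, admits a pre-active P4 value in the two Placebo/linzagolix columns, and the SAP contains conflicting signals rather than a rule that excludes it. That the sample is pre-active rests on the protocol's order of events at Month 6; the SAP does not restate it for P4.

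A reader might infer that the switch-group proportions are necessarily inflated. The documents do not support that. The direction is fixed only among women with at least one post-dose sample, and even there the increase may be zero; women with only a Month 6 sample can pull the figure either way. Nor can a size be claimed: the documents give no P4 rates and say of enrolment only that it was substantially below target. The 10-point figure and the illustrative ranges rest on assumptions.

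The consequence is confined to one descriptive proportion in a study with no hypothesis tests. By-visit P4 from Month 7 and the hormone listing (Listing 16.2.8.5.1) remain, so the count can be redone by hand.

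**What to change.** In SAP section 4.8.4 and Table 14.4.6.3, count only P4 samples taken after the first extension dose up to Month 12, in all four groups. Include on-treatment early-termination and unscheduled samples, selected by date relative to the first extension dose rather than by assigned visit, so that an early post-dose sample is not lost to the Month 6 window. Use women with at least one such sample as the denominator, state per group how many have none, and retitle the table to say that the window runs from after the first extension dose to Month 12.

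Showing Month 6 values above 10 nmol/L separately is optional. In 4.8.10, align the Month 6 wording with the Month 7 start of Table 14.4.15.1.

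The cost is one sentence, one date filter on data already collected, a table title and one word in 4.8.10. There are two downsides: women without a post-dose sample leave the denominator, which is why their number must be shown, and the continuing groups lose one on-drug sample from this count.

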# Cytel

## Statistical Analysis Plan

Sponsor:	ObsEva		
Protocol:	19-OBE2109-00	5	
Document Version No.:	1.0	Document Date:	18-MAY-2021

- LDL ≥ 190 mg/dL
- HDL < 40 mg/dL

will be reported at each visit.

Shift tables from baseline and shift tables from baseline 2 (only for the subjects who are in the placebo arm in the main study) to each visit will be provided for the following LDL and Triglycerides categories (after rounding to integer values if necessary).

LDL:

- 0: ≤ 130 mg/dL
- 1: 131 to 159 mg/dL
- 2: 160 to 189 mg/dL
- 3: ≥ 190 mg/dL

Triglycerides:

- 0: ≤ 150 mg/dL
- 1: 151 to 300 mg/dL
- 2: 301 to 500 mg/dL
- 3: 501 to 1000 mg/dL
- 4: >1000 mg/dL

All laboratory data will be provided in data listings. Day 1 Serum levels of the anti-müllerian hormone (AMH) and fasting glucose will be included in the listings.

A subset listing will be presented for all abnormal clinically significant laboratory values.

## 4.8.5. Vital Signs and Physical Examinations

Vital signs include: Height (cm), Weight (kg), Body Mass Index, Systolic Blood Pressure (mmHg), Diastolic Blood Pressure (mmHg) and Heart Rate (beats/min).

Height is assessed at Screening (main study); Weight is assessed at Month 6, Month 9, Month 12, as well as at M3 ExtFU and M6 ExtFU visits. Other Vital Signs are assessed at every monthly visit during the extension treatment period and at Month 1, 3 and 6 from the extension follow-up period.

Physical Examination was to be assessed Month 6, Month 9, Month 12, as well as at M3 ExtFU and M6 ExtFU visits.

Sponsor:	ObsEva		
Protocol:	19-OBE2109-00	5	
Document Version No.:	1.0	Document Date:	18-MAY-2021

The actual value, change from baseline and change from baseline 2 (only for the subjects who are in the placebo arm in the main study) for each on-study evaluation will be summarized by treatment group for vital signs.

By-subject listings of vital sign measurements will be presented in data listings.

Physical examination results at each time point will be summarized by treatment group; Shifts from Baseline and shift from baseline 2 (only for the subjects who are in the placebo arm in the main study) in physical examination findings to each on study visit will also be presented.

All physical examination findings will be presented in a data listing.

### 4.8.6. Electrocardiogram

Local 12-lead ECG readings of QTcF are performed at every monthly visit during the extension treatment period, as well as Months 1,3 and 6 from the extension follow-up period.

Baseline will be defined as the highest QTcF value prior to first dose of the main study.

Baseline 2 will be defined as the highest QTcF value prior to first active dose of the extension study from screening to Month 6 (only for subjects in the placebo arm of the main study).

The actual value, change from baseline and change from baseline 2 (only for the subjects who are in the placebo arm in the main study) of ECG results will be summarized descriptively, as well as the number and percent of subjects with normal, abnormal and clinically significant abnormal results at each study visit by treatment group.

All ECG data for each subject will be provided in data listings.

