10.5 LINZAGOLIX AND KP017 PLASMA LEVELS

PK blood samples will be collected from each subject at each study visit during the Treatment Period for determining linzagolix and KP017 plasma levels.

At the visits where IMP intake is at site, i.e. at Months 6, 7, 8, 9, 10 and 11 visits, PK sampling will be performed before IMP intake. The approximate time of dose administration on the four previous days and time of PK sampling will be recorded in the eCRF.

In case of early discontinuation visit, PK sampling is not required at the withdrawal visit if the subject had no IMP administration the day prior to the withdrawal visit.

Details of the blood sampling process, sample handling and shipment are described separately in a laboratory manual provided by the central laboratory.

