Liver function tests: following the Food and Drug Administration (FDA) guidance on drug-induced liver injury (8), subjects who have an elevation of hepatic enzymes are to be withdrawn immediately from treatment if:

- ALT or AST >8xULN
- ALT or AST >5xULN for more than 2 weeks
- ALT or AST >3xULN and (TBL >2xULN or INR >1.5)

• ALT or AST >3xULN with the appearance of fatigue, nausea, vomiting, right upper quadrant pain or tenderness, fever, rash, and/or eosinophilia (>5%)

Withdrawn subjects will be followed up until hepatic parameters return to normal.

ECG: subjects who have a QTcF > 500 ms or increase > 60 ms from the highest value prior to the first dose in the main study will have to be withdrawn from study treatment and followed up until return to QTcF < 480 ms or – if not reached after 3 months of treatment cessation- be referred to a cardiologist. They will enter the 6-month Follow-Up Period and undergo the follow-up ECGs according to the schedule of events.

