Appendix A. Schedule of study assessments – Treatment Period

¹ All visits should take place at the end of the defined period (i.e. M7 visit should be scheduled at the end of Month 7, M8 visit should be scheduled at the end of Month 8, etc.). All visit dates should be calculated from the date of Day 1 visit (in the main study). A month is defined as 28 days/4 weeks. Visits should be scheduled ± 3 days (-3/+ 2 days for Month 7 visit) from the calculated date.

² All Month 6 assessments except informed consent and inclusion/exclusion criteria would have been performed as part of the main study (18-OBE2109-002 - Edelweiss 2).

³ ECG should be performed at about the same time but before the PK sample

 $^4~$ If endometrium thickness in TVUS is $\leq 5~$ mm, no endometrial biopsy will be necessary.

⁵ Overnight fasting is required.

 $^{6}\,$ Only for subjects who met the following criterion at any site on the M6 DXA scan: -2.5 < Z-score \leq -1.5

Schedule of study	assessments -	Treatment 1	Period ((cont'd)
e e e				· /

Schedule of study assessments – Treatment Period							
Timing ¹	Treatment Period						
	M6 ²	M7	M8	M9	M10	M11	M12
IMP accountability	X	X	X	X	X	X	X
Dispense linzagolix/placebo kit	X	X	x	x	x	X	
Dispense ABT/placebo kit	X			х			
EHP-30, EQ-5D-5L and PROMIS ³	x	x		x			x
mPGIS, PGIC, HRUQ and HRPQ ³	X	х	х	х	X	х	Х
SSIQ and PSIQ ³	x						X
Blood sample for PK ⁴	X	х	х	х	X	X	Х
E2, LH, P4	X	X	x	X	X	x	x
SHBG	X			x			X
Bone biomarkers	X			х			Х

¹ All visits should take place at the end of the defined period (i.e. M7 visit should be scheduled at the end of Month 7, M8 visit should be scheduled at the end of Month 8, etc.). All visit dates should be calculated from the date of Day 1 visit (in the main study). A month is defined as 28 days/4 weeks. Visits should be scheduled ± 3 days from the calculated date.

² All Month 6 assessments except informed consent and inclusion/exclusion criteria would have been performed as part of the main study.

³ ClinROs (PSIQ and HRUQ) will be administered to the subject by the site staff and the responses will be filled in the eDiary. ePROs (EHP-30, EQ-5D-5L, PROMIS, PGIS, PGIC, HRPQ and SSIQ) will be filled in by the subject in the eDiary.

⁴ PK samples should be taken after the ECG and before the daily dose of IMP.

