#### 4.2.11. Baseline Definitions

The baseline will be described in two ways:

- Main Baseline, defined in the Statistical Analysis Plan of the main study and calculated according to first dose of IMP taken during the main Study.
- Second Baseline (named Baseline 2), defined as the last assessment before the first active dose of IMP during the extension study. The baseline 2 will be calculated only for the subjects who are in the placebo arm (actual arm) in the main study.

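### QTcF change is measured from the highest earlier reading, which biases mean change downward and makes the Baseline and Baseline 2 changes non-comparable

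*SAP*

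**What the plan says.** SAP 4.8.6 gives QTcF its own baselines. For all subjects, "Baseline will be defined as the highest QTcF value prior to first dose of the main study". For those who switched from placebo to linzagolix, "Baseline 2 will be defined as the highest QTcF value prior to first active dose of the extension study from screening to Month 6". It then summarises "The actual value, change from baseline and change from baseline 2" by visit and treatment group. The planned output is "Table 14.4.9.1 ECG QTcF by Visit from Month 7 up to Month 6 Extension Follow-up" (SAP 7.2).

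The general rule in SAP 4.2.11 is different: Baseline 2 is "defined as the last assessment before the first active dose of IMP during the extension study". Neither 4.8.6 nor SAP Section 5 explains why ECG departs from it.

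In the protocol, the highest earlier value serves as a reference for individual subjects, in exclusion criterion 5c and in the withdrawal rule of 10.7.2.1. The withdrawal rule is triggered by a QTcF above 500 ms or an "increase > 60 ms from the highest value prior to the first dose in the main study".

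**The concern.** A maximum is a sensible reference for a per-subject alarm, because it makes a false trigger less likely. It is a poor reference for a mean. The highest of several readings is partly high by chance, and a later single reading will on average fall below it. The mean change is then pulled down before any drug effect is considered.

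The amount depends on how many readings feed the maximum. Baseline 2 uses a longer window than Baseline, so the two change summaries for the same ex-placebo subjects are pulled down by different amounts. The same applies when change from Baseline 2 in those subjects is set beside change from Baseline in the continuous-linzagolix groups.

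Cardiac safety including QT prolongation is a stated safety objective (Protocol 6.2), and the SAP has been narrowed to safety. Protocol 5.5.1 describes a borderline QTc effect, exceeding the threshold of concern by less than 2 msec, so shifts of a few milliseconds matter. No placebo arm continues, so nothing concurrent cancels the shift. It errs towards reassurance and is largest for Baseline 2, in subjects whose first linzagolix exposure is in this study.

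**Working it through.** The plan states no QTcF SD, bias or power, so there is no figure of its own to reproduce.

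**1. Number of readings, k.**

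- Baseline: one or more. SAP 4.5.1 lists QTcF among the main-study baseline variables, and the withdrawal rule needs a value before first dose. The number is not stated.
- Baseline 2: all the Baseline readings plus later main-study ECGs up to Month 6. The Month 6 ECG is scheduled, and "All Month 6 assessments except informed consent and inclusion/exclusion criteria would have been performed as part of the main study" (Protocol Appendix A). It also precedes extension dosing: Appendix A puts the ECG before the PK sample, and at visits with on-site dosing, Month 6 included, "PK sampling will be performed before IMP intake" (Protocol 10.5). The planned minimum is therefore k = 2.

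**2. Ordering.** The Baseline 2 window contains the Baseline window. Baseline 2 ≥ Baseline in every subject, so change from Baseline 2 ≤ change from Baseline at every visit. This follows from the definitions alone.

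**3. Expected bias.** Write each earlier reading as m + eᵢ and the on-study reading as m + d + e₀. Here m is the subject's own level, d the drug effect, and the errors are independent normal with SD σ and no time trend. Then

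E[change from maximum] = d − σ × Eₖ,

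where Eₖ is the expected maximum of k independent standard normals: E₁ = 0, E₂ = 1/√π = 0.564, E₃ = 3/(2√π) = 0.846, and, by numerical integration, E₇ = 1.352 and E₈ = 1.424.

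Assumed σ is 5 to 12 ms. The cases k = 7 and 8 suppose six monthly main-study ECGs up to Month 6 on top of one or two before first dose. That is also an assumption.

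| k | Eₖ | Understatement, σ = 5 ms | Understatement, σ = 12 ms |
|---|---|---|---|
| 1 | 0 | 0 | 0 |
| 2 | 0.564 | 2.8 | 6.8 |
| 3 | 0.846 | 4.2 | 10.2 |
| 7 | 1.352 | 6.8 | 16.2 |
| 8 | 1.424 | 7.1 | 17.1 |

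**4. Gap between the two change columns, same subjects, same visit.** Gap = σ × (E for Baseline 2 − E for Baseline).

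| Baseline k | Baseline 2 k | Difference in E | σ = 5 ms | σ = 12 ms |
|---|---|---|---|---|
| 1 | 2 | 0.564 | 2.8 | 6.8 |
| 2 | 3 | 0.282 | 1.4 | 3.4 |
| 2 | 8 | 0.860 | 4.3 | 10.3 |
| 1 | 7 | 1.352 | 6.8 | 16.2 |

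**5. Simulation check.** This used 400,000 subjects, σ = 10 ms, k = 2 for Baseline and k = 8 for Baseline 2.

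| True effect | Change from Baseline (maximum) | Change from Baseline 2 (maximum) | Change from last reading, either baseline |
|---|---|---|---|
| 0 ms | −5.7 | −14.2 | 0.0 |
| +10 ms | +4.3 | −4.2 | +10.0 |

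The zero-effect row agrees with the formula (0.564 × 10 = 5.6; 1.424 × 10 = 14.2). The mean of the pre-dose readings was also unbiased.

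**The case against.** The strongest reply concerns size and consequence.

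- **Size.** Neither σ nor the main-study ECG counts are in the documents. The upper figures need monthly main-study ECGs, which nothing available here confirms. Positive serial correlation between a subject's readings would shrink the expected maximum. With one reading before first dose, Baseline is unbiased. Visits were sometimes remote during COVID-19, so some ex-placebo subjects may lack a Month 6 ECG. All of this stands: k = 2 for Baseline 2 is the planned minimum, not a certainty for each subject, and the result is a direction with a range.
- **Consequence.** The study stopped early with few subjects, and there is no hypothesis test. Actual values and ECG findings are summarised, and every ECG is listed. The by-visit table also runs into the off-drug follow-up, and on-drug versus off-drug change within the same subjects is not shifted. This limits the severity, but listings do not correct a misleading summary column.
- **Rationale.** Extending the highest-value idea to the first active dose parallels the withdrawal rule, which SAP 2.3.1 restates without naming the main study. An analysis baseline also need not match a withdrawal threshold. But the protocol ties that rule to the first main-study dose for every subject, so a maximum running to Month 6 serves no protocol criterion. The parallel does not remove the bias either.
- **Remedy.** SAP 4.2.11 gives the last-assessment rule for Baseline 2 only and leaves the main Baseline to the main-study SAP, which is not available here. A count against the 60 ms criterion is in neither listed ECG table. Both points are correct and are allowed for in the fix.

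**Conclusion.** The concern holds and should be fixed. As defined, change from Baseline 2 can never exceed change from Baseline, and it is biased downward wherever the scheduled Month 6 ECG was recorded. Change from Baseline is biased downward wherever a subject had two or more ECGs before first main-study dose.

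With an assumed within-subject SD of 5–12 ms and independent, trend-free readings, the understatement for Baseline 2 is 2.8–6.8 ms at the planned minimum of two readings and 6.8–17.1 ms at seven or eight. For Baseline it is 0 with one reading, 2.8–6.8 ms with two and 4.2–10.2 ms with three. With no drug effect, the two columns would differ on average by 1.4–3.4 ms (k = 2 and 3) up to 6.8–16.2 ms (k = 1 and 7).

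Confidence is high in the direction; the size rests on these assumptions. The damage is confined to the change-from-baseline summaries.

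**What to change.** In SAP 4.8.6 and Table 14.4.9.1, compute QTcF change from the last pre-dose value or from the mean of the pre-dose values, with the same rule for Baseline and Baseline 2. The last value already agrees with 4.2.11 for Baseline 2. For Baseline, check the main-study SAP, and footnote any difference from its ECG tables.

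Keep the highest value before the first main-study dose only as the reference for the protocol's existing individual criterion (QTcF above 500 ms, or a rise of more than 60 ms from that value), and label it so. If subjects meeting that criterion are to be counted, this is one small additional output.

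The cost is two sentences in 4.8.6 and one derivation change, plus that count if wanted. No new data are required.
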